Clinical Study Design:	
This is a prospective, longitudinal, non-interventional, multi-center study to collect subject and physician satisfaction, and treatment experience with Dysport in real clinical practice in subjects of Chinese origin.
 
Approximately 250 subjects are planned to be included in the study to receive three injection cycles with Dysport in the GL. The decision by the physician to treat the subject with Dysport on a long term basis must be made before including the subject in the study, and has to be clearly separated and independent of the decision to include the subject in the study.
 
Given the non-interventional nature of the study, subject visits, treatment regimen, and the administration of Dysport to treat GL will be carried out according to the physician's real clinical practice and the approved leaflet in China.
 
The study consists of three injection cycles. Each injection cycle includes an injection visit and a follow up visit three weeks later (\pm 7 days). Following the 1st injection at Visit 1, subsequent injections, i.e., 2nd injection and 3rd injection, will be scheduled three to six months apart. The final follow up visit will be held three to six months after the subject's 3rd injection.
 
The screening visit and the 1st injection visit may be conducted on the same day. Data will be collected at all visits, if held. Subjects and physicians, independent of each other, will assess the subject's GL severity, and will complete a questionnaire about satisfaction with treatment outcomes at all visits.
 
Injection practice details for each injection visit, including muscle(s) injected, total dose and volume, dose and volume per injection point, and number of injection points will be collected per the study objectives.
 
Adverse events (AEs) will be collected during the study.

Total Number of Subjects (Planned):	
Approximately 250 subjects will be included in the study.
 
To avoid bias in the recruitment of subjects, physician will be asked to include all consecutive subjects during Botulinum toxin A (BoNT-A) consultations to achieve the recruitment target of 20-30 subjects during a restricted and defined period. If consecutive inclusions are not feasible (e.g., administrative constraints), and in order not to disturb the medical activities in the physician's clinic, physician will be authorized to space the inclusions (e.g. inclusion of one subject after every two, or three, etc.), and will follow the same recruitment frequency until achievement of the recruitment target. The modalities for recruitment will have to be determined prior to recruitment start.

Number of Clinical Study Centers (Planned):	10 study centers

Effective date: 2021-06-28 08:30

Effective

2.0

		
Region(s) / Country Involved (Planned):	China	
Clinical Study Duration:	
The planned clinical study duration is approximately 24 months.
 
The planned duration of recruitment is approximately six months.
	
Duration of Subject Participation:	In accordance with the treatment regimen and the physician's real clinical practice, study participation for each subject is anticipated to be approximately nine to 18 months.	
Inclusion Criteria:	
 1. Adult male or female up to 65 years of age, and of Chinese origin. 2. Moderate (grade 2) or severe (grade 3) glabellar lines at max frown as assessed by the physician using the CC1 3. Prior to and independent of study, subject is seeking long term treatment of their glabellar lines. 4. Prior to and independent of the study participation, physician intended to treat the subject with Dysport. 5. Time and ability to complete the study and comply with instructions. 6. Understands the study requirements and signed the informed consent form (ICF). 	
Exclusion Criteria	
 1. Hypersensitive to Dysport or its excipients. 2. Presence of contraindications to Dysport treatment as specified in the approved leaflet in China. 3. Subject is at risk for precautions, warnings, and/or contraindications to Dysport as specified in the approved leaflet in China 4. Subject has an infection in the proposed treatment area. 5. Subjects has had treatment failure experience with other toxins. 6. Pregnant or breast feeding female, or female intending to get pregnant during the study. 7. Participation in a clinical study, interventional or non-interventional, within 30 days prior to study entry (signature of informed consent). 	
Treatment:	
This is a non-interventional study (NIS). The decision by the physician to treat the subject with Dysport on a long term basis must be made before including the subject in the study, and has to be clearly separated and independent of the decision to include the subject in the study.
 
Commercially available Dysport will be used in the study but will not be supplied by the study Sponsor. The physician is free to choose Dysport modalities of administration in accordance with the local SmPC and the approved leaflet in China.
	

Effective date: 2021-06-28 08:30

Effective

2.0

		
	
Product: Commercially available Dysport, a BoNT-A product.
 
Strength/Concentration: 300 units (U) per vial
 
Reconstitution Volume: 1.5 milliliter (mL)
 
Dosage (total dose per treatment): 50 U total (0.25 mL total) 10 U per injection site (0.05 mL per injection site)
 
Route: Intramuscular injection
 
Treatment Regimen: Three injection cycles, 3-6 months apart
 
Location of Treated Area: Glabellar region
	
	
Efficacy Assessments: Efficacy assessments include:
 
 • Subject Satisfaction Questionnaire • Subject assessment of GL severity at max frown using the 4-point Categorical Scale • Physician Satisfaction Questionnaire • Physician assessment of GL severity at rest and max frown using the Investigator's 4-point Photographic Scale • Injection practice details 	
	
Primary Objective and Endpoint: The primary objective of the study is to evaluate subject satisfaction after three injection cycles with Dysport in the GL.
 
At Visit 6 (i.e., three weeks, \pm 7 days, after the 3rd injection) subjects will be asked "What is your overall satisfaction after three treatment cycles with Dysport?" See Appendix 1 Question 17.
 
Response options:
 
 • Very Satisfied • Satisfied • Dissatisfied • Very Dissatisfied 
The primary endpoint will evaluate the proportion of subjects in each response category.
	
	
Secondary Objectives and Endpoints: The secondary efficacy objectives and endpoints of the study are:
 
 1. Objective: To evaluate physician satisfaction after three injection cycles with Dysport in the GL. 
Endpoint: Proportion of subjects in each response category for the physician's overall satisfaction with Dysport after three injection cycles will be evaluated at Visit 6 (i.e., three weeks, \pm 7 days, after the 3rd injection). See Appendix 2, Question 7.
 
 2. Objective: To evaluate subject CCI after each injection cycle with Dysport in the GL. 
Endpoints:
 
 a. Proportion of subjects in each response category per question answered on the Subject Satisfaction Questionnaire complete at all visits. See Appendix 1. 
CCI
	

CONFIDENTIAL

Page 10 of 58

Effective

Effective date: 2021-06-28 08:30

 GALDERMA		
	CCI	
Safety Assessment:	
AEs will be collected during the study. AE data will be recorded in the electronic case report form (eCRF) for inclusion in the clinical database.
 
In addition to AEs, physicians will report any Adverse Drug Reaction (ADR), Unexpected ADR (UADR), Serious Adverse Event (SAE), Special Situation (SS) and pregnancy events to CCI [REDACTED] in accordance with regulatory requirements and timelines. The data will be included in the global drug safety database.
	
Statistical Methods:	
In general, efficacy, safety, and baseline characteristics variables will be presented using descriptive statistics and graphs, as appropriate. Continuous endpoints will be summarized using descriptive statistics (e.g., mean, median, standard deviation, minimum and maximum values). Categorical endpoints will be presented in frequency tables with number and percentage of observations for each level.
 
95% confidence intervals (CIs) will be calculated whenever appropriate.
	
Sample Size:	
The sample size of approximately 250 subjects is not based on a statistical calculation. The selected number of subjects is regarded as sufficient for an evaluation of the studied endpoints by using descriptive statistics.
	
Analysis:	
Since this is an open non-interventional study, available data may be analyzed prior to study completion.
	

2021-06-28 08:30

Effective date:

Effective

2.0

CLINICAL STUDY SCHEMATIC AND FLOW CHART

[figure not shown]
Table 1 Clinical Study Schematic

	Physician decision to treat the subject with Dysport on a long term basis
	↓
	Screening/Baseline/1 st Injection
	↓
Treatment	Commercially available Dysport
Treatment Frequency	Three injection visits, three to six months apart (Visits 1, 3, 5) ↓
Follow up Visits	A follow up visit occurs three weeks (\pm 7 days) after each injection visit (Visits 2, 4, 6) Final follow up visit occurs three to six months after the 3 rd injection (Visit 7)

Effective date: 2021-06-28 08:30

Figure 1 Study Flow Chart

Effective

2.0

 GALDERMA	Title Clinical Study Protocol 05PF2009 NIS Dysport China	Doc id
---	--	--------

SCHEDULE OF ASSESSMENTS

Table 2 Schedule of Assessments

Visit Number	Injection Cycle 1		Injection Cycle 2		Injection Cycle 3		Visit 7
	Visit 1 ¹	Visit 2	Visit 3	Visit 4	Visit 5	Visit 6	
Visit Name	Screening Baseline/ Injection 1 ¹	Follow up 1	Injection 2	Follow up 2	Injection 3	Follow up 3	Follow up 4
Visit Window	≤ 30 days of Baseline/Injection 1	3 weeks (± 7 days) from Injection 1	3-6 months from Injection 1	3 weeks (± 7 days) from Injection 2	3-6 months from Injection 2	3 weeks (± 7 days) from Injection 3	3-6 months from Injection 3
Informed Consent	X						
Demographic Data	X						
Medical History	X						
Safety Review	X	X	X	X	X	X	X
Injection Practice Details	X		X		X		
Physician GL Severity Assessment	X ²	X	X ²	X	X ²	X	X
Physician Satisfaction Questionnaire	X ²	X	X ²	X	X ²	X	X
Subject assessments							
Subject GL Severity Assessment	X ²	X	X ²	X	X ²	X	X
Subject Satisfaction Questionnaire	X ²	X	X ²	X	X ²	X	X

Definitions:

- 1 month = 4 weeks

1. Screening and Baseline/Visit 1 (i.e., Injection 1) may be performed on the same day. If performed as separate visits, informed consent, demographic data, and medical history should be complete at Screening, and all other remaining visit procedures and confirmation of subject medical history should be performed at Baseline /Visit 1 (i.e., Injection 1).
2. Prior to injection.

Effective

Effective date: 2021-06-28 08:30

LIST OF ABBREVIATIONS AND DEFINITIONS OF TERMS

Abbreviation	Term
°C	Degrees Celsius
ADR	Adverse Drug Reaction
AE	Adverse Event
BoNT	Botulinum toxin
BoNT-A	Botulinum toxin serotype A
CI	Confidence interval
eCRF	electronic Case Report Forms
CRO	Contract Research Organization
CSP	Clinical Study Protocol
CTA	Clinical Trial Agreement
e.g.	For Example (Latin: exempli gratia)
etc.	Et cetera
G	Gauge
GL	Glabellar lines
GCP	Good Clinical Practice
HSA	human serum albumin
ICH	International Council for Harmonisation
i.e.	That is (Latin: id est)
IEC	Independent Ethics Committee
ICF	Informed Consent Form
mL	Milliliter
N/A	Not Applicable
NIS	Non-interventional study
NMPA	National Medical Products Administration
p	Page(s)
PP	Per-Protocol
PQC	Product Quality Complaint
QA	Quality Assurance
RA	Regulatory Authority
SAE	Serious Adverse Event
SAP	Statistical Analysis Plan
SS	Special Situation
U	Units
UADR	Unexpected Adverse Drug Reaction

Note: Physician and Investigator are synonymous and used interchangeably throughout the CSP.

2.0

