Ipsen is the marketing holder of *Dysport*, a BoNT-A product, which is currently licensed in over 75 countries worldwide, and it was approved by the National Medical Products Administration of China (NMPA) in 2020. It is indicated for the temporary improvement in the appearance of moderate to severe glabellar lines (GL) caused by the activity of corrugator or *musculus procerus* in adult patients not more than 65 years of age. To achieve a clinical effect, a total of 50 units (U) is given intramuscularly in five equal aliquots of 10 U each into each of five sites, two in each corrugator muscle and one in the procerus muscle. Re-treatments should be administered no more frequently than every three months.

Controlled clinical trials in China demonstrated the short and long term efficacy and safety of *Dysport* in the treatment of the GL; however, there is a lack of scientific data related to subject and physician reported outcomes. The rationale for the current study is to collect subject and physician satisfaction, and long term treatment experience with *Dysport* in the GL in subjects of Chinese origin in a real-life clinical setting.

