1.2 Drug Profile

Dysport contains a neurotoxin complex that is produced by fermentation of *Clostridium botulinum* bacteria toxin type A, Hall strain. This haemagglutinin complex is composed of a number of proteins naturally produced along with the toxin which is believed to stabilize it but which has no apparent therapeutic effect in its own right. *Dysport* contains nominally 300 U of BoNT-A-haemagglutinin

complex together with 125 µg of human serum albumin (HSA) and 2.5 mg of lactose in a clear glass vial. Further details can be found in the approved leaflet in China.⁴

Dysport is labelled for a dose of 50 U to be injected intramuscularly in five equal aliquots of 10 U each into each of five sites, two in each corrugator muscle and one in the procerus muscle. Retreatment is permitted every three months.⁴

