1.3 Risk/Benefit Assessment

In placebo-controlled clinical trials of *Dysport*, very common adverse reactions (> 1/10) following injection were injection site reactions (e.g. erythema, oedema, irritation, rash, pruritus, paraesthesia, pain, discomfort, stinging and haematoma), and headache. Common reactions (> 1/100) included eye disorders (e.g., asthenopia, eyelid ptosis, eyelid oedema, lacrimation increased, dry eye, muscle twitching (twitching of muscles around the eyes), and facial paresis (due to temporary paresis of facial muscles proximal to injection sites, it is predominantly manifested as brow paresis).⁴

Side effects related to spread of toxin distant from the site of administration have been reported, such as dry mouth, excessive muscle weakness, dysphagia, aspiration pneumonia, with fatal outcome in some very rare cases. Hypersensitivity reactions have also been reported post-marketing.⁴

The dose administered and the minimum time between treatments are according to the approved leaflet in China. Steps to reduce complications of ptosis are outlined in Section 6.1.5. Subject will be provided with information on the benefits and risks of their treatment by the physician in accordance with their real clinical practice.

The risks associated with participation in this study are considered acceptable compared to the anticipated high degree of subject and physician satisfaction with treatment and the treatment regimen.

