8.1.5 Special Situation (SS) Events

A Special Situation (SS) event is an incidence of overdose, off-label use, medication error, occupational exposure, abuse, misuse or lack of therapeutic efficacy while using the medicinal product, or any instance of drug exposure during pregnancy or breast-feeding. A SS should be reported even if it is not associated with an adverse event.

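### Does counting a month as four weeks let re-injection start before the protocol's own three-month minimum?

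*Protocol*

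**What the plan says.** The schedule of assessments (Protocol Table 2, repeated in SAP Section 3.3) gives the second injection as "3-6 months from Injection 1" and the third as "3-6 months from Injection 2". Beneath the table, under its definitions, both documents state "1 month = 4 weeks".

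Three other places in the protocol deal with the interval between treatments:

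- Section 1.1: "Re-treatments should be administered no more frequently than every three months".
- Section 1.2, citing the leaflet: "Retreatment is permitted every three months".
- Section 1.3: "The dose administered and the minimum time between treatments are according to the approved leaflet in China".

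None of these three says how a month is counted. Section 9.1.3 also tells sites to book the next visit three to six months from the injection, with no definition at that point. Section 4 expects each subject to take part for about nine to 18 months. Section 8.1.5 names "overdose, off-label use, medication error" among the Special Situations, which are reportable even without an adverse event.

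**The concern.** A reader who takes three months in Sections 1.1 to 1.3 to be calendar months sees the schedule opening the re-injection window several days before the protocol's own minimum interval. An injection in that gap would be in window and yet might count as off-label use, hence a reportable Special Situation. At the other end, a subject who returns at six calendar months would be outside the window.

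Two things would be at stake. One is the spacing of a toxin treatment and how early re-injections are reported. The other is the per-protocol set: SAP Section 7.1.1 bases efficacy primarily on the PPS, and Section 6.2 removes subjects with major deviations. If a window miss counted as major, the meaning of a month would help decide who is in the primary efficacy set.

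**Working it through.** The documents give no day count for the window, so there is no stated figure to reproduce. The inputs are the three-to-six-month window and the four-week month (Protocol Table 2, SAP Section 3.3) and the nine-to-18-month participation (Protocol Section 4). The comparator is an assumption: the number of days to the same date three or six calendar months later, for every start date from 1 January 2021 to 31 December 2024.

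**Window edges**

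| Edge | Four-week month | Calendar months | Difference |
|---|---|---|---|
| Opens | 3 × 28 = 84 days | 89 to 92 days (mean 91.3) | 5 to 8 days |
| Closes | 6 × 28 = 168 days | 181 to 184 days (mean 182.6) | 13 to 16 days |

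Days 84 to 88 are thus always in window and always short of three calendar months. For some start dates this extends to day 91.

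**Participation.** There are three intervals: injection 1 to 2, injection 2 to 3, and injection 3 to Visit 7.

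- Shortest: 3 × 84 = 252 days = 36 weeks; 252 / 28 = 9 four-week months.
- Longest: 3 × 168 = 504 days = 72 weeks; 504 / 28 = 18 four-week months.
- In calendar months, 252 / 30.44 = 8.3 and 504 / 30.44 = 16.6.

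The nine to 18 months in Section 4 is what the four-week definition gives. A shortfall appears only if one side of the comparison is converted to calendar months and the other is not.

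**Do the passages contradict each other?**

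- If the months in Sections 1.1 to 1.3 are four-week months, the minimum is 84 days and matches the opening of the window.
- If they are calendar months, days 84 to 88 fall inside the schedule and before that minimum.

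Nothing in either document selects the second reading.

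**What depends on it?**

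- *Treatment.* Section 1.3 ties the minimum interval to the leaflet. Sections 3, 6.1.5, 6.1.5.2, 6.4 and 9.1 also make treatment subject to it. The visit window does not authorise an injection that the leaflet would not.
- *Special Situations.* Whether an injection is off-label is judged against the label, so the definition under Table 2 does not alter that judgement. Being both compliant and reportable is no contradiction: lack of efficacy is also a Special Situation and can occur in a fully compliant subject.
- *PPS.* An injection on days 84 to 88 is in window and creates no deviation from Table 2. A late one could, but Protocol Section 10.1.2 names only non-completion and eligibility violations as grounds for exclusion. SAP Section 6.2 leaves exclusions to the data review meeting before database lock.
- *Primary endpoint.* The question is asked at Visit 6, three weeks (± 7 days) after injection 3. Neither that timing nor the exact interval for each proportion uses the gap between injections.

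**The case for a change.** The best case for a change runs as follows. A note under a study table cannot decide what three months means in an external leaflet, and the four-week month is missing from the protocol's list of definitions. Physicians are told to follow both the leaflet and Table 2, and nothing says the two count months in the same way. The upper edge does not depend on the leaflet at all: a site following Section 9.1.3 and booking six calendar months lands 13 to 16 days outside the window. That is a realistic booking, since Section 1.1 puts the usual duration of effect at about four to six months. The SAP's criterion of good overall compliance also leaves room to exclude such subjects, and a line of clarification costs almost nothing.

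The ambiguity stands, and so does the arithmetic at both edges. The consequences do not. The leaflet conflict is conditional on a source that is not in the documents. A late return is compatible with visits that follow ordinary practice, and no rule makes it a major deviation. If the data review meeting did exclude such subjects, SAP Section 7.4.1 reports the primary endpoint on the FAS as well, so the effect would be visible. Applying one window to both deviation and Special Situation checks would be a step backwards: the documents give no maximum label interval, so late returns would be flagged as Special Situations without any basis.

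**Conclusion.** No change follows. This is a counting convention that the plan does not spell out everywhere, and the study team can apply it sensibly. Questionnaires carry a completion date and are filled in before treatment at injection visits, so the interval in days can be derived for each subject. The data review meeting can then treat window departures consistently before database lock.

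The possible discrepancy is 5 to 8 days at the lower edge and 13 to 16 days at the upper edge, and it exists only if the undefined months are calendar months. If they are four-week months, it is zero. The documents do not show how many subjects would fall in the affected days. The primary estimate and the sample size do not depend on the answer, and no effect on safety or on PPS membership has been shown.

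The conclusion rests on two readings: that treatment stays subject to the leaflet, as the protocol says repeatedly, and that a mistimed injection visit is not automatically a major deviation, since neither document makes it one. If the sponsor's own check showed that the leaflet counts months differently from Table 2, those passages would have to be reconciled. Which interval is right is not a matter for this review.

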1 BACKGROUND AND RATIONALE

1.1 Medical Background and Short Rationale for the Clinical Study

Botulinum toxin (BoNT) is a potent neurotoxic protein produced by the Gram-positive anaerobic bacterium, *Clostridium botulinum*. The molecule is produced naturally by these bacteria together with a series of accessory proteins, forming what is termed the “toxin complex”. The neurotoxin is the cause of the severe and potentially fatal disease of botulism. In addition, the protein is used in very small quantities as a treatment modality for aesthetic and medical indications, many of which are characterized by increased muscle activity. Botulinum toxins occur in seven known serotypes (A-G) that are produced by different strains of *Clostridium botulinum*. Clinically important biologic activity is limited primarily to the A and B serotypes, of which the type A serotype (BoNT-A) is used widely throughout the world for the treatment of a range of clinical conditions. BoNT-A blocks the release of acetylcholine into the neuromuscular junction (synapse) cleft, thereby prohibiting the activation of acetylcholine receptors. Paresis by chemical denervation thus occurs in the target muscle, leading to inhibition of muscular contraction.

In the early 1990s, patients treated with BoNT-A for blepharospasm were observed to lose their frown lines,^{1,2} and since publishing these observations, the use of BoNT-A in the aesthetic setting has accelerated. Injectable BoNT-A products have been investigated for multiple aesthetic indications in attempts to reverse the appearance of aging, especially in the facial region.¹ In the treatment of facial lines, the effect of BoNT-A injections usually persists for approximately 4-6 months. Facial muscle activity and severity of the facial wrinkles then returns to baseline. Full functionality of facial muscles is usually restored by approximately 6 months post-treatment.³

Ipsen is the marketing holder of *Dysport*, a BoNT-A product, which is currently licensed in over 75 countries worldwide, and it was approved by the National Medical Products Administration of China (NMPA) in 2020. It is indicated for the temporary improvement in the appearance of moderate to severe glabellar lines (GL) caused by the activity of corrugator or *musculus procerus* in adult patients not more than 65 years of age. To achieve a clinical effect, a total of 50 units (U) is given intramuscularly in five equal aliquots of 10 U each into each of five sites, two in each corrugator muscle and one in the procerus muscle. Re-treatments should be administered no more frequently than every three months.

Controlled clinical trials in China demonstrated the short and long term efficacy and safety of *Dysport* in the treatment of the GL; however, there is a lack of scientific data related to subject and physician reported outcomes. The rationale for the current study is to collect subject and physician satisfaction, and long term treatment experience with *Dysport* in the GL in subjects of Chinese origin in a real-life clinical setting.

